3.5. Duration of Subject Participation

Subjects will participate in a screening visit and, if eligible, will participate in the study for up to 13 days (\pm 2 days).

4. STUDY POPULATION

4.1. Subject Recruitment

Subject recruitment will abide by the guidelines of the IRB and the investigational site(s). Recruitment will continue until enrollment requirements are met, including reaching the targeted number of subjects completing the study procedures with adequate data collection. A subject will be considered enrolled if he/she has signed a consent form and participant has passed all screening criteria.

Investigators will keep a record, i.e. subjects screening log, of subjects who are entered into the study. Each subject must meet all the inclusion criteria and none of the exclusion criteria for this study at the time of screening and study participation. The Sponsor must approve any changes to the target distribution of subjects in writing prior to enrollment.

4.2. Study Cohorts and Target Population

The study will include 4 cohorts of subjects:

- Cohort 1 will include subjects with no known history of AF*
- Cohort 2 (Aggressor Rhythm Cohort) will include subjects with no known history of AF*, but with history of frequent premature atrial contractions (PACs), frequent premature ventricular contractions (PVCs), supraventricular tachycardia (SVT), or non-sustained ventricular tachycardia (NSVT)
- Cohort 3 (non-permanent AF) will include subjects with known history of paroxysmal, persistent, or chronic AF*
- Cohort 4 (permanent AF) will include subjects with permanent AF.

* History of AF encompasses the 2 years prior to participation in study screening procedures.

For all cohorts, the following age, gender, and race/ethnicity enrollment targets will be adhered to during subject recruitment:

- A minimum of 10% of subjects will be enrolled in the age category of <55 and a minimum of 20% in the age categories of 55 to 64, and ≥65 years.
- At least 40% of subjects in Cohort 1 will be female and at least 40% male. At least 20% of subjects in each of Cohorts 3 and 4 will be female and at least 20% will be male.
- At least 10% of subjects in Cohort 1 will be non-Caucasian. In Cohorts 3 and 4 as a combined group, at least 10% of subjects will be non-Caucasian.

The incidence of AF is known to increase with age, male gender, and White race (Benjamin, 2019). These recruitment targets are also consistent with the subject population observed in the Apple Heart Study, which is representative of the intended use population (Turakhia, 2019).

Table 1 identifies the estimated number of subjects targeted for enrollment. A minimum of [REDACTED] subjects will be enrolled in Cohort 2.

Table 1: Targeted Number of Enrolled Subjects Per Cohort

Cohort 1 (NSR)	Cohort 2 (Aggressor Rhythm Cohort)	Cohort 3 (non-permanent AF)	Cohort 4 (permanent AF)
[REDACTED]	[REDACTED]	[REDACTED]	[REDACTED]

Abbreviations: NSR = normal sinus rhythm

While subjects will be recruited based upon known inclusion/exclusion criteria including history of arrhythmia, there is uncertainty on whether the presentation of that rhythm will present and occur during study based on the natural temporal variability of heart rhythms. Thus, study enrollment will continue until minimum targets based on rhythm presentation during study is achieved across all cohorts; enrollment may cease after minimum targets are achieved.

Enrollment for Cohort 1 will continue until the target number of enrolled subjects are achieved as in Table 1.

Enrollment for Cohort 2 will continue until minimum numbers of subject enrolled complete the study with presentation of aggressor rhythms as determined by ECG patch are reached, as specified in Table 2A.

Enrollment in Cohorts 3 and 4 will continue during the study until minimum targets of burdens are achieved as in [Table 3B](#). Atrial fibrillation burden for each subject in the self-reported enrollment Cohorts 3 and 4 will be determined from the ambulatory ECG Patch reference device after subjects complete and/or terminate from the study. A final AF cohort assignment will be determined based on this adjudicated AF burden measurement. Enrollment for Cohort 4 will continue until minimum numbers with $\geq 95\%$ AF burden as determined by ECG patch are reached.

[Table 3B](#) identifies the minimum number of subjects in Cohorts 3 and 4 required to exhibit the level of AF burden as determined by ECG patch after the subject completes and/or terminates from the study:

Table 2A: Cohort 2 Minimum Aggressor Rhythm Targets

Presence of Aggressor Rhythm on ECG Patch
[REDACTED]

Table 3B: Cohort 3 and 4 Minimum AF Burden Targets

Total AF burden >0% to <95%	AF burden >0% to 33%	AF burden >33% to <95%	AF burden $\geq 95\%$ to 100%
[REDACTED]	[REDACTED]	[REDACTED]	[REDACTED]

4.3. Inclusion Criteria

Subjects must meet all the following inclusion criteria to be enrolled:

1. Able to read, understand, and provide written informed consent

2. Willing and able to participate in the study procedures as described in the consent form
3. Be 22 years of age and older
4. Able to communicate effectively with and follow instructions from the study staff
5. Able to wear the wrist device for duration of study participation
6. For Cohort 1, have no known medical history of AF
7. For Cohort 2, have no known medical history of AF and active diagnosis of at least one of the following arrhythmias within the past 2 years:
 - a. Frequent PACs, defined as at least 1% of total beats of atrial ectopic beats by 24-48 hour Holter, ambulatory ECG monitor, or implantable loop recorder) OR evidence of such by 12-lead ECG.
 - b. Frequent PVCs, defined as at least 1% of total beats of ventricular ectopic beats by 24-48 hour Holter, ambulatory ECG monitor, or implantable loop recorder OR evidence of such by 12-lead ECG.
 - c. SVT, which will include atrial tachycardia, atrioventricular nodal re-entrant tachycardia, atrioventricular re-entrant tachycardia by 12-lead ECG or 24-48 hour Holter, ambulatory ECG monitor, or implantable loop recorder,
 - d. NSVT, defined as three or more consecutive ventricular beats at a rate of at least 100 beats per minute and lasting no more than 30 seconds, by 12-lead ECG or 24-48 hour Holter, ambulatory ECG monitor, or implantable loop recorder
8. For Cohorts 3 and 4, have a known diagnosis of AF at the time of screening (confirmed by electronic medical record (EMR) or self-report) and have had a recent episode of AF, or confirmed AF on ECG, in the past 12 months
9. For Cohort 4, have a known diagnosis of permanent AF at the time of screening (confirmed by EMR or self-report) and have had a recent episode of AF, or confirmed AF on ECG, in the past 12 months
10. Meet additional binning based on demographics.

4.4. Exclusion Criteria

Subjects who meet any of the following criteria may not be enrolled:

1. Physical disability that precludes safe and adequate testing
2. Mental impairment resulting in limited ability to cooperate
3. Known uncontrolled medical conditions, such as (but not limited to) significant anemia, important electrolyte imbalance and untreated or uncontrolled thyroid disease
4. Open wound(s) on the wrist and/or forearm
5. Tattoos, large moles, or scars on the wrist at the wrist device location
6. Skin conditions on either wrist that would preclude subject from wearing a wristband on either wrist

7. Known allergy or sensitivity to medical adhesives, isopropyl alcohol, wristbands, or ECG patch
8. Medical history or physical assessment finding that makes the subject inappropriate for participation according to investigator(s)
9. Participation in a previous study that used a wrist-worn sensor device with a simultaneous ECG reference patch
10. Implantable cardiac devices such as a Pacemaker or Implantable Cardioverter Defibrillator
11. Clinically significant hand tremors, as judged by the investigator
12. Acute illness including COVID and other respiratory illnesses
13. Subjects with known history of AF on rhythm control medications with history of complete AF rhythm control (i.e history of zero AF burden) will be excluded from Cohorts 3 and 4

Subjects enrolled into Cohort 2 can be on rate control medications.

4.5. Subject Discontinuation

Subject participation in the study is voluntary and the subject has the right to withdraw at any time. Subjects also may be withdrawn from the study without their consent.

Reasons for possible subject discontinuation may include:

- Adverse event
- Death
- Protocol deviation
- Withdrawal of consent
- Investigator discretion
- Termination of the study
- Device malfunction
- Lost to follow-up
- Other

Sites will notify Sponsor of the reason(s) for subject discontinuation. Site investigators must also report this to their respective IRBs, as defined per their IRB procedures.

4.6. Subject Follow-up

A follow-up visit will be conducted at Study Day 13 (\pm 2 days), or after the conclusion of the 2nd ECG patch wear period, if less than 13 \pm 2 days, during which the subject will return the wrist devices and ECG patch to the site. Following the completion of procedures at this visit, the subject's participation in the study will be concluded.

5. STUDY PROCEDURES

Table 4 outlines the procedures to be conducted and the information to be collected during the study.

Table 4: Schedule of Events

Study Procedure	Screening	Study Day 1 Visit	Study Day 5 (+2 days) Visit	End of Study Visit*
Informed Consent	X			
I/E Criteria Assessment	X			
Medical History including allergies	X			
Demographic information (age, gender, race/ethnicity, occupation)	X			
Medications	X			
Physical examination (will include at a minimum visual inspection of general appearance and skin)	X			
Body Measurements and Assessments (anthropometrics) (height, weight, BMI; may be self-reported)	X			
Wrist/Hand Assessment (tattoos, moles, scars, skin tone assessment on Fitzpatrick scale)**	X	X		
Distribution of 2 wrist study devices to subject		X		
Application of ECG patch to subject's upper torso		X		
Replacement of ECG patch			X	
Collection of 2 wrist study devices from subject				X
Removal of ECG patch from subject				X
Collection of all AEs encountered during the study		X	X	X

* End of study visit is on Day 13 (\pm 2 days), or after the conclusion of the 2nd ECG patch wear period, if less than 13 ± 2 days.

**Skin tone assessment on Fitzpatrick scale confirmed on Study Day Visit 1.

5.1. Screening

Informed consent will be obtained before any study protocol-directed procedures are performed. After the signing of informed consent, the subject will be evaluated for eligibility according to the study inclusion/exclusion criteria (Section 4.3 and Section 4.4). This visit will be conducted remotely; in-person, on-site visits can occur only if approved by Sponsor.

During screening, the following should be obtained on each subject:

- Age
- Gender
- Race and ethnicity
- Diagnosed medical conditions
- Medications
- Allergies
- Occupation
- Visual assessment of general appearance and skin
- Body measurements and assessments (height, weight, BMI)*
- Skin tone assessment on Fitzpatrick scale
- Assessment of tattoos, moles, scars on wrist (both)

*Body measurements may be self-reported if the screening visit is conducted virtually.

5.2. Study Day 1

Subjects will report for the Day 1 visit at their scheduled date and time, which may be the same day as the screening visit if conducted in-person, on-site, but in no case more than 14 days after the screening visit. No special preparation for this visit is required. If eligibility is confirmed after completion of all screening procedures, subjects may begin study participation following the screening. This visit will be conducted remotely; in-person, on-site visits can occur only after Sponsor approval.

All subjects may take their normal medications on the day of the study and may eat normally prior to this visit.

Skin tone assessment on the Fitzpatrick scale will be confirmed at this visit.

5.2.1. Data Collection Study Equipment Set up

The following procedures will be performed for each study subject at study participation:

Two wrist devices of the same series/configuration will be assigned to each subject for the study. The first wrist device will be worn during the day for daytime data collection. The second wrist device will be worn during the night for nighttime data collection during sleep. The wrist devices are to be charged while not being worn.

1. Instruct the subject to choose his/her preferred wrist to wear the wrist device. The wrist device can be worn on whichever side the subject prefers unless there is a skin condition on one wrist as noted above in the exclusion criteria, in which case, the wrist device must be worn on the non-affected wrist. Record the chosen wrist. If the subject does not have a side preference or skin condition on one wrist, the wrist device will be placed on the left wrist.
2. The subject will be asked to put the wrist device on his/her wrist (as indicated in 1). The wrist device should be fitted tightly enough that it does not move when the hand/wrist is shaken.
3. Ask user to adjust band tightness for a snug fit and adjust as needed.

An ECG patch will be self-applied to the upper torso of the subject on Day 1 and Day 5 (+2 days) of the study. Self-application of ECG patch may be performed with aid of instructions via televideo. If the visit is occurring on site, the study staff may assist with the patch placement.

5.3. Study Days 1-13

Subjects will continue to wear the wrist devices and patch as directed during normal daily activities for up to 13 (\pm 2) days. This includes pressing a button on the patch to confirm that the patch is still working properly. Follow up calls or telehealth video calls may be made to the subject as needed throughout the home use period. Subjects will be advised to not swim or do activities that will cause excessive sweating.

5.4. Study Day 5

Subjects will remove the 1st ambulatory ECG patch on study Day 5 (+2 days). A 2nd ECG patch will be self-applied to the subject. If the visit is occurring on site, the study staff may assist with the patch placement. The 1st patch will be returned to study staff. This visit will be conducted remotely; in person on-site visits can occur only after Sponsor approval.

5.5. End of Study Visit

Thirteen days (\pm 2 days) after the initial study visit, or after the conclusion of the 2nd ECG patch wear period, if less than 13 \pm 2 days, subjects will have a follow-up visit to be exited from the study. Wrist devices, study phones and the second ECG patch will be returned to the CRO. Following the completion of procedures at this visit, the subject's participation in the study will be concluded. This visit will be conducted remotely; in-person, on-site visits can occur only after Sponsor approval.

5.5.1.1. Study Procedures

The following study procedures will be performed at this visit/contact:

1. Subjects will be asked to report any study procedure-related adverse events (AEs) that occurred during the previous 13 days (\pm 2 days), or during the ECG patch wear periods if less than 13 \pm 2 days.
2. The subject's second ECG patch will be returned to staff. ECG patch data will be downloaded by study staff for processing and adjudication (Section [5.5.2](#)).

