	
assessment of tattoos, moles, scars on wrist (both), and skin tone assessment on Fitzpatrick scale.
 
Day 1:
 
• This visit can be done remotely, or in person following Sponsor approval. This visit should be no more than 14 days after screening• Two (2) wrist devices of the same series and configuration will be assigned to each subject (one for daytime wear and one for wear during sleep) at random from the set of wrist device series/configurations included in this study. Two iPhones will also be assigned to each subject.• The single-lead ambulatory ECG patch will be affixed to the subject's upper torso per manufacturer's instructions and using standard procedures.• Skin tone assessment on the Fitzpatrick scale will be confirmed. 
Day 5 (+ 2 days):
 
• This visit can be done remotely, or in person following Sponsor approval• Study staff will be in contact with the subject to execute replacing the subject's ECG patch.• The ECG patch will be returned to study staff for download 
Day 13 (\pm 2 days), or end of 2nd ECG patch wear period, if less than 13 \pm 2 days:
 
• This visit can be done remotely, or in person following Sponsor approval• Subjects will be asked to report any study procedure-related adverse events (AEs) that occurred during the previous period of up to 13 days (\pm 2 days), or during the ECG patch wear periods if less than 13 \pm 2 days.• The subject's ECG patch will be removed. The ECG patch data will be returned to the study staff for processing and adjudication. 
The investigational Irregular Rhythm Notification Feature (IRNF) 2.0 and Atrial Fibrillation Burden Feature (AFBF) 1.0 algorithms (test devices) will be run post-hoc on the sensor dataset to generate tachograms and notification. The performance of each test device will be determined based upon adjudication of concurrent data from the reference device.

--	---

Duration of Study Participation	
 Up to 13 ± 2 days, or until the end of the 2nd ECG patch wear period, if less than 13 ± 2 days

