6.2.4. Safety Analyses

All adverse events (AEs) will be recorded throughout the entire study period, whether they are considered to be related to the study procedures or not. Signs and symptoms of each AE will be described in detail: date of event, description of event, severity, relationship to study procedures, action taken and outcome. AEs will be collected as spontaneously reported by the subjects.

AEs will be coded using MedDRA (latest version). The number of any AEs and the number and percentage of subjects reporting each type of adverse event will be presented by Preferred Term. Multiple occurrences of the same event reported by the same subject will be counted only once.

AE summaries (number of events and incidence) will be presented for all AEs, including the following:

- Serious adverse events (SAEs)
- Study procedure related AEs
- Severe AEs, which are AEs that are rated as Severe in intensity

Study procedure related AEs will include those events classified as possibly or definitely related to the study procedure.

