7.1.1. AE/SAE Collection

Any abnormal laboratory findings, abnormal safety assessments, or anticipated day-to-day fluctuations which are associated with a pre-existing disease or condition, are not considered an adverse event unless judged by the investigator to be worsening or more severe than expected. All adverse events must be fully recorded throughout the entire study period, whether they are considered to be related to the study procedures or not. Adverse events will be collected as spontaneously reported by the subjects.

Adverse events should be followed until they are resolved or stabilized (returns to baseline for a pre-existing condition) and followed by a private MD, or the subject is lost to follow-up. In the event of a subject not returning to the clinical unit, the outcome of this event will be recorded as lost at follow up.

Possible AEs include the following:

- Skin rash on wrist due to wearing the wrist device;
- Pressure artifacts on wrist due to wearing the wrist-sensor device;

The following occurrences are not to be regarded as AEs:

- Underlying (pre-existing) symptoms or diseases, unless there is an increase in severity or frequency during the course of the investigation;
- Detection of atrial fibrillation or other irregular heartbeat;
- Complaint about wrist device functionality.

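### The end-of-study question on adverse events is limited to procedure-related events, which conflicts with the plan's own requirement to collect, record and summarise all adverse events

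*Combined protocol and SAP*

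**What the plan says.** The combined protocol and SAP describes adverse event collection in several places, and they do not agree on scope.

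- **Synopsis, Study Procedures, Day 13:** "Subjects will be asked to report any study procedure-related adverse events (AEs) that occurred during the previous period of up to 13 days".
- **Section 5.5.1.1:** "Subjects will be asked to report any study procedure-related adverse events (AEs", over the previous 13 ± 2 days, with the patch-wear periods as the window if these are shorter.
- **Section 5, Table 4 (Schedule of Events):** the row "Collection of all AEs encountered during the study" is marked at the Day 1, Day 5 and End of Study visits.
- **Section 6.2.4:** "All adverse events (AEs) will be recorded throughout the entire study period, whether they are considered to be related to the study procedures or not". Summaries are planned for all adverse events, with serious, procedure-related and severe events also shown. The procedure-related group takes in events classed as possibly or definitely related.
- **Section 7.1.1:** "All adverse events must be fully recorded throughout the entire study period", again regardless of relatedness. The definition in Section 7.1 does not depend on relatedness either.
- **Sections 7.1.2 and 7.1.3:** the investigator determines relatedness.
- **Mode of collection:** Section 6.2.4 states that "AEs will be collected as spontaneously reported by the subjects", and Section 7.1.1 says the same.

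**The concern.** The visit text puts one question about adverse events to the subject, and that question already contains a judgement of relatedness. The plan gives this judgement to the investigator, after the event has been reported. A site can carry out Section 5.5.1.1 exactly as written and still not deliver what Table 4 and Sections 6.2.4 and 7.1.1 require.

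Two summaries could be affected. The all-event table would combine events that were asked about with events that were merely volunteered. The procedure-related table could also lose entries, because an event that the investigator would class as possibly related may never be mentioned by a subject who thinks it unrelated.

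Several features of the study make the answer to this question matter:

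- Visits are remote unless the sponsor approves otherwise (Sections 5.1, 5.2, 5.4 and 5.5).
- Table 4 schedules the physical examination at screening only, and the wrist and hand assessment at screening and Day 1 only. No skin inspection is scheduled at exit, although Section 1.4 names rash and skin irritation as risks.
- Participation ends after this visit (Sections 4.6 and 5.5), so no later scheduled contact would recover an event missed there.

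**Working it through.** The plan states no figure on this point, so the check is a comparison of the passages.

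**Step 1. Scope at the end-of-study visit**

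| Place | Events in scope | Mode |
|---|---|---|
| Synopsis, Day 13 | Procedure-related | Subject is asked |
| Section 5.5.1.1 | Procedure-related | Subject is asked |
| Table 4, End of Study column | All | Not stated |
| Section 6.2.4 | All, related or not | Spontaneous report |
| Section 7.1.1 | All, related or not | Spontaneous report |

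The first two rows agree with each other and differ in scope from the other three. Because the restriction appears in both the synopsis and the body, it does not look like an isolated slip.

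**Step 2. Does any other visit text ask a wider question?** The synopsis entries for Day 1 and Day 5, and Sections 5.2, 5.2.1 and 5.4, contain no adverse event question. Section 5.3 allows calls as needed but does not say what is asked. Table 4 says that all events are to be collected at these visits, but not how. The restricted question is therefore the only one in the visit text.

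**Step 3. Who decides relatedness?** Sections 7.1.2 and 7.1.3 assign this to the investigator. The restricted question moves a first sift to the subject.

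**Step 4. What could be lost?** Let U be the number of subjects whose adverse events are all unrelated, and c the share of them captured without being asked.

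- Subjects missing from the all-event count: (1 − c) × U.
- If sites follow Table 4 and Section 7.1.1 in full, c = 1 and the loss is (1 − 1) × U = 0.
- If no unrelated event is ever volunteered, c = 0 and the loss is (1 − 0) × U = U.

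The documents give neither U nor c, so the loss can only be bounded between 0 and U.

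**Step 5. Who is exposed?** The full analysis set, which Section 6.8 uses for safety, targets 235 to 627 subjects according to the synopsis. About 40 sub-study subjects follow the same procedures (Section 3.1) and have their own adverse event summary (Section 6.8). These are the numbers of people who would be asked the question, not estimates of missed events.

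**The case against.** The strongest reply is that the protocol, read whole, already orders collection of all events at this visit. Neither the synopsis nor Section 5.5.1.1 says that nothing else is asked. Table 4 marks all-event collection in the same visit column, and Section 7.1.1 makes full recording mandatory. Section 1.4 says subjects will be encouraged to tell staff about injuries, side effects or discomfort arising during participation or because of it, so unrelated events are not wholly unprompted. The case report forms are not in the file, and what staff actually ask is unknown.

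Much of this stands. A reader might infer that unrelated events will be missed and that the all-event table will certainly be incomplete. The documents do not support that: a site following Table 4 and Section 7.1.1 loses nothing. A reader might also infer that serious events will go unreported. The documents do not support that either, because Section 7.1.2 sets a separate reporting route, within 24 hours of the investigator's awareness and without regard to relatedness. And since Sections 1.4 and 7.1.1 name rash among the expected events, a skin reaction that the subject takes to be unrelated is possible but not a compelling example.

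The wording on spontaneous reporting need not contradict asking a question. It can mean events described in the subject's own words and not drawn from a symptom checklist. It is unclear beside a targeted question, but it is compatible with an open one.

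Finally, this is a non-significant-risk study with no randomised treatment and no safety hypothesis, so no comparison of treatments can be biased.

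None of this removes the conflict over scope. Table 4 states what to collect, whereas the visit text states what the subject is asked, and the two differ.

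**Conclusion.** The synopsis and Section 5.5.1.1 conflict with Table 4 and with Sections 6.2.4, 7.1 and 7.1.1 on which adverse events are in scope at the last visit. They also sit badly with Sections 7.1.2 and 7.1.3 on who judges relatedness. This is an internal inconsistency with a possible consequence for ascertainment.

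The consequence rests on one assumption: that some sites follow the visit text and not Table 4. Under that assumption the all-event table may be under-counted, and so may the possibly related category within the procedure-related table. The size cannot be determined from the documents and could be zero. It is confined to descriptive safety summaries; the IRNF and AFBF performance endpoints do not depend on it. It is worth correcting because the correction is small and would make the planned all-event table match the way the data are collected.

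**What to change.** 1. In the synopsis (Day 13) and Section 5.5.1.1, delete the qualifier that limits the question to procedure-related events. Have subjects asked one open, non-leading question about any adverse event over their whole participation.
2. Keep the existing recall window of 13 ± 2 days, or the patch-wear periods if shorter. Do not replace it with the time since the last contact. The Day 5 text contains no adverse event question and calls are made only as needed, so a shorter window could leave earlier days uncovered.
3. Leave relatedness to the investigator, as Sections 7.1.2 and 7.1.3 already provide.
4. In Sections 6.2.4 and 7.1.1, align the statement on spontaneous reporting with this question, for example by saying that events are recorded as the subject describes them in answer to an open question or volunteers them at any time.

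The cost is a wording change in four places and slightly more adverse event entries. Section 8.1 requires IRB approval of an amendment before it is implemented. The statistical analyses do not change.
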